**Table 2 Time windows for pain intensity assessments (VAS and Likert)**

Nominal time	Time window	
	Start time (h)	End time (h)
Baseline		≤0
6 h	>0	≤9
12 h	>9	≤15
18 h	>15	≤21
24 h	>21	≤30
36 h	>30	≤42
48 h	>42	≤60
72 h	>60	≤84
Day 5	>84	≤108
Each following day until Day 15 but day 15 does not have an end.	+24	+24

Abbreviations: h, hours; VAS, Visual analogue scale.

If IMP is not taken the following rules will be used:

- For the first flare, for patients not receiving treatment the baseline VAS pain measurement from their date of randomization will be used as the baseline assessment.
- For subsequent flares, if a patient doesn't receive treatment, the flare will not be accounted for.

If multiple assessments fall within the same windows the following rules will be used:

- If multiple assessments fall into the same time window, the one closest to the nominal time will be used.
- If multiple assessments in the same time window are equidistant to the nominal time, the latest will be used.
- If multiple assessments have the exact timestamp, an average will be used.

### **18.17 Pain intensity on Visual analogue scale (VAS)**

The patients will score their current pain intensity in the joint most affected (i.e., the index joint) on a continuous 0 to 100 VAS, ranging from no pain (0) to unbearable pain (100). The original 100 mm scale has been transferred into ePRO format and proportionally scaled down to 5 cm in length. The conceptual equivalency of the pen-and-paper and the ePRO format has been tested and is described in a Cognitive Debriefing and Usability Testing of Pain Scales for Gouty Arthritis Report.

For each flare, the pain intensity will be assessed in the index joint and recorded in the patient diary prior to the first IMP administration. Subsequent pain assessment will be recorded in the patient diary at 6, 12, 18, 24, 36, 48, and 72 hours and Days 5, 6, 7, 8, 9, 10, 11, 12, 13, 14 and 15. At 24, 48, and 72 hours and Day 5, the assessments will take place just before IMP administration. If the time point for a specific assessment occurs during sleep, pain intensity will be recorded just before and after sleep, and the assessment closest to the scheduled time point will be used in the analysis (see Section 18.16).

For each time point (6, 12, 18, 24, 36, 48, and 72 hours and Days 5, 6, 7 and 8), the change from baseline in pain intensity on VAS is defined as:

$$\text{VAS pain intensity at specific time point} - \text{VAS pain intensity at baseline}$$

### **18.18 Pain intensity on Likert**

In addition to the VAS scale, the patients will score their current pain intensity in the index joint on a 5-point Likert scale (0 to 4 point scale: “none”, “mild”, “moderate”, “severe”, “extreme”).

For each flare, the pain intensity will be assessed in the index joint and recorded in the patient diary prior to the first IMP administration. Subsequent pain assessment will be recorded in the patient diary at 6, 12, 18, 24, 36, 48, and 72 hours and Days 5, 6, 7, 8, 9, 10, 11, 12, 13, 14 and 15. At 24, 48, and 72 hours and Day 5 the assessments will take place before IMP administration. If the time point for a specific assessment occurs during sleep, pain intensity will be recorded just before and after sleep, and the assessment closest to the scheduled time point will be used in the analysis.

For each time point (6, 12, 18, 24, 36, 48, and 72 hours and Days 5, 6, 7 and 8), the change from baseline in pain intensity on Likert is defined as:

$$\text{Likert pain intensity at specific time point} - \text{Likert pain intensity at baseline}$$

### **18.19 Onset of effect**

Onset of effect is defined as  $\geq 20\%$  change from baseline pain intensity on VAS, and time to onset of effect is defined as the first time point after first IMP injection when this is observed using all measurements at all actual timepoints. The percentage of change from baseline in pain intensity on VAS is defined as:

*(VAS pain intensity at specific time point – VAS pain intensity at baseline) / (VAS pain intensity at baseline)*

## **18.20 Response**

Response is defined as  $\geq 50$  % change from baseline pain intensity on VAS, and time to response is defined as the first time point after first IMP injection when this is observed using all measurements at all actual timepoints. The percentage of change from baseline in pain intensity on VAS is defined as:

*(VAS pain intensity at specific time point – VAS pain intensity at baseline) / (VAS pain intensity at baseline)*

## **18.21 Resolution of pain**

Resolution of pain is defined as  $< 10$  in pain intensity on VAS, and time to resolution of pain is defined as the first time point after first IMP injection when this is observed using all measurements at all actual timepoints.

## **18.22 Time to rescue medication**

Intake of rescue medication is recorded by the patient using the eDiary:

101 = Acetaminophen

102 = Paracetamol

103 = Acetaminophen/Codeine

104 = Paracetamol/Codeine

105 = Codeine

106 = Tramadol

(107 = Ice/cold-pack will not be counted as rescue in the time to rescue calculation)

108 = Other (non medicinal products will not be counted as rescue)

If other is selected the type will be recorded in the Rescue Medication in the eCRF. Patients still having insufficient relief with the rescue medication listed above after the 72 hour assessment are allowed to take glucocorticoids which can be recorded in the Rescue Medication form or Concomitant Medication form in the eCRF. If a patient has taken glucocorticoids, but has no earlier intake of rescue medication from the list, the glucocorticoid intake will be counted as rescue.

The date and time when the first rescue medication is taken in either system will be used in the calculation of time to intake of rescue medication, defined as (in hours):

*Date/time of intake of first rescue medication – date/time of intake of first IMP*

In case of incomplete or missing date and/or time for either occasion, the following rules will be applied:

- If the minute is missing, the time will be set to the full hour before, i.e. HH:00. If this imputation gives a time point that is prior to the first dose of IMP, the time will be set to the same time point as the first IMP injection.
- If both the hour and minutes are missing, the time will be set to 00:00.
- In the event of missing date, timing of rescue medication cannot be assessed and this recording will not be included in the analysis.
- For glucocorticoids captured as concomitant medication where only date and no timing information is available time is set to 00:00

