7.4.6.3 Administration

The IMP administration will be initiated on the day of randomization (Visit 1) and the administrations scheduled for the first day of each flare will be supervised or given by the investigator (or delegated study staff) at the out-patient clinic, emergency department (ED) or hospital. If the patient is treated by an out-patient clinic or is discharged from ED/hospital before the end of 5-day IMP administration period, the daily s.c. injections at 24, 48 hours and Day 5 will be administered at home by the patient themselves or a caregiver.

At the 72-hour visit (Day 4, Visit 2), the IMP administration will be supervised or given by the investigator.

Instructions on appropriate use should be given by the investigator to the patient or caregiver. Patients or caregivers should not be allowed to administer any IMP until the patient or caregiver has demonstrated a thorough understanding of procedures and an ability to inject the IMP correctly. A patient leaflet with detailed instructions on the handling, injection and disposal of IMP will be handed out.

Anakinra and matching placebo

The IMP should be administered using subcutaneous injections into fat tissue.

The used syringes should be disposed of and the patients will receive disposal boxes for at home use.

Triamcinolone and matching placebo

For systemic therapy, injection should be made deeply into the gluteal muscle. For adults, a minimum needle length of 1½ inches is recommended. In obese patients, a longer needle may be required.

Throughout each treatment period, the actual number of IMP administrations and timepoint of each administration will be recorded in the eCRF or the patient diary.

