## **18 Derived and computed variables**

### **18.1 Unpermitted rescue medication**

Unpermitted rescue medication that leads to exclusion from PP population is defined as more than one incorrect intake, i.e. either type or outside time window (multiple incorrect intakes within 15 minutes is counted as one):

- Unpermitted type
  - Types other than paracetamol/acetaminophen and/or codein or tramadol or rescue medications classified as non-medicinal products (e.g. ice/cold pack, vinegar) and taken between treatment start and 72 hours.
  - Glucocorticoids (from general concomitant medication and rescue medication) taken between treatment start and 72 hours).
  - All unresolved OTHER <72 hours.

- Outside time window
  - All rescue (from rescue medication) taken prior to the 24 hours VAS pain assessment. If 24 hours VAS pain is missing, taken within 24 hours since treatment start.
  - All rescue (from rescue medication) taken within 6 hours prior to the 48 hours VAS pain assessment. If 48 hours VAS pain is missing, taken within 42 to 48 hours since treatment start.
  - All rescue (from rescue medication) taken within 6 hours prior to the 72 hours VAS pain assessment. If 72 hours VAS pain is missing, taken within 66 to 72 hours since treatment start.
  - All rescue (from rescue medication) with a missing timestamp (date and time) that can be related to a flare.

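### SAP 18.22: a rescue intake dated Day 1 with no clock time gets a negative time to rescue, because the reset to the first dose covers only missing minutes

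*SAP*

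**What the plan says.** SAP 18.22 defines the event time as "Date/time of intake of first rescue medication – date/time of intake of first IMP", in hours. It then lists imputation rules, introduced by "In case of incomplete or missing date and/or time for either occasion, the following rules will be applied". Four matter here:

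- **Minute missing:** the time goes back to the full hour. A safeguard follows: "If this imputation gives a time point that is prior to the first dose of IMP, the time will be set" to that of the first injection.
- **Hour and minutes missing:** "If both the hour and minutes are missing, the time will be set to 00:00". No safeguard follows.
- **Glucocorticoids without a clock time:** "For glucocorticoids captured as concomitant medication where only date and no timing information is available time is set to 00:00". No safeguard follows here either.
- **Date missing:** the record is left out of the analysis.

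SAP 14.3.1.5 uses the event time for the first flare in a stratified log-rank test with a Peto hazard ratio and in a time-to-event graph. It also tabulates rescue use by interval: from the first IMP to 12 hours, then to 24, 48 and 72 hours, Day 8 and Day 15.

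On timing of the first dose, Protocol 7.4.6.3 states: "The IMP administration will be initiated on the day of randomization (Visit 1"). Protocol 7.4.9 has its date and clock time entered in the eCRF.

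**The concern.** The safeguard is worded for the imputation in its own bullet, where going back to the full hour shifts a time by less than one hour. The two rules that go back to midnight can shift a time by most of a day, and they have no safeguard. Because patients are dosed during Day 1, midnight of Day 1 precedes the dose, and the subtraction gives a negative number.

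A time to event measured from first dose cannot be negative. Neither SAP 14.3.1.5 nor 18.22 says whether such a value is kept, set to zero or excluded. The choice would fall to the programmer, although the SAP is meant to be final before the first database lock. If the value is excluded, patients who took rescue soonest after dosing leave the analysis of how soon rescue was needed. If the interval tables use the same derived time, as the reference to 18.22 in 14.3.1.5 suggests, these patients also belong to no interval, since the first one begins at the first IMP.

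**Working it through.** **Inputs.** The formula and rules are those of SAP 18.22. The documents contain no dosing times, so first doses from 08:00 to 22:00 on Day 1 are an assumption. The plan states no figure on this point to reproduce.

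**Formula.** For a record with a date but no clock time, time to rescue = 24 × (day number − 1) − clock hour of the first dose.

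| First dose | Day 1 record | Day 1 with reset | Day 2 record | Day 3 record | Day 4 record |
|---|---|---|---|---|---|
| 08:00 | -8 h | 0 h | 16 h | 40 h | 64 h |
| 10:00 | -10 h | 0 h | 14 h | 38 h | 62 h |
| 14:00 | -14 h | 0 h | 10 h | 34 h | 58 h |
| 18:00 | -18 h | 0 h | 6 h | 30 h | 54 h |
| 22:00 | -22 h | 0 h | 2 h | 26 h | 50 h |

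Only Day 1 records go negative, so the reset changes nothing from Day 2 on. The exceptions on Day 1 are a dose given at exactly 00:00, or a first dose whose own clock time is missing and is also set to 00:00; both give 0 h.

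**The rule that has the safeguard.** With a first dose at 10:30 and an intake recorded only as hour 10, the imputed time is 10:00. The difference is 10:00 − 10:30 = -0.5 h, which is reset to 0 h. The reset therefore removes an error of half an hour here, while an error of 8 to 22 hours under the other two rules stands.

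**What one record is worth in the log-rank test.** As an illustration, ignore the strata, use the planned 106 anakinra and 53 triamcinolone patients, take anakinra as group 1 and suppose one event at the earliest time:

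- Expected events in group 1: 106/159 = 0.667.
- Contribution to U: 1 − 0.667 = 0.333 if the patient is on anakinra, or 0 − 0.667 = -0.667 if on triamcinolone.
- Contribution to V: 0.667 × 0.333 = 0.222.

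The contribution is the same whether the time is -14 h or 0 h, because either value ranks first. It is lost if the record is dropped.

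**The case against.** The strongest reply is that the case is rare. Rescue is permitted only after the 24-hour assessment (Protocol 7.5.5.4, SAP 4.1), so Day 1 intake is a deviation. The same protocol section asks for date and time of every intake, so the clock time must be missing as well. The one source that the SAP expects to be date-only, glucocorticoids on the concomitant medication form, is permitted only after 72 hours. All of this stands and keeps the point small. It does not make the rule right: the SAP provides for missing hours, and it tabulates rescue in the first 12 hours, so it expects some such records.

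A reader might infer more than the documents support:

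- **That 'Other' rescue is often date-only.** In SAP 18.22, 'Other' is an eDiary code; only its type goes to the eCRF.
- **That permitted intake becomes unpermitted and removes patients from the PP population.** SAP 18.1 lists "Glucocorticoids (from general concomitant medication and rescue medication) taken between treatment start and 72 hours", but it does not say that it uses the 18.22 imputed time, and it has its own rule for missing timestamps. Exclusion also needs more than one incorrect intake. For a 14:00 dose, Day 4 at 00:00 is 58 h and Day 5 at 00:00 is 82 h. Day 5 at 00:00 is after 72 h for any Day 1 dose (96 minus an hour below 24). A course begun on Day 4 thus has at most one misplaced date.
- **That events are put in the wrong order and the reset cures it.** With a 14:00 dose and a true intake at 20:00 (+6 h), -14 h ranks first and so does 0 h. The reset removes an impossible value, but not the imputation error.
- **That date-only Day 4 glucocorticoids should be moved to after the 72-hour assessment.** That would assume adherence and could hide real early use. Midnight is a uniform earliest-time convention, and a glucocorticoid sets the event time only where no listed rescue came before it.

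**Conclusion.** The point holds as a drafting gap. Read literally, SAP 18.22 gives any Day 1 rescue record without a clock time a negative time to rescue: -8 to -22 hours for assumed dosing between 08:00 and 22:00. No rule in the SAP sections on this endpoint deals with that value. Its presence in the missing-minute rule suggests that the safeguard was left out of the other two by oversight.

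The consequence is minor. It concerns time to first rescue, a secondary endpoint, with its hazard ratio, graph and interval tables. The primary endpoint is untouched. The number of records cannot be estimated from the documents but is probably low. Loss of early rescue users from the log-rank test depends on how negative times are programmed; the SAP does not say that they are dropped. The absence of a valid value and of a matching interval does not depend on that choice.

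**What to change.** In SAP 18.22, make the existing safeguard a general rule for all imputed times, including both 00:00 rules: where the result precedes the first dose, "the time will be set to the same time point as the first IMP injection". Add to SAP 14.3.1.5 that these patients stay in the stratified log-rank analysis as events at time 0, and that time 0 belongs to the first tabulated interval. The second addition matters because that section leaves out patients censored at baseline, and a time-0 event should not be confused with them.

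The cost is one or two sentences and a line of code. It needs no new data, changes no time from Day 2 onward, and follows the SAP's own convention.

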### 18.23 Drug exposure

Drug exposure will be calculated as the total amount IMP (mg) given for each flare and for the total study.

For each flare, the patient should receive 11 syringes. At Visit 1 (Day 1), 1 injection of triamcinolone or placebo and 2 injections of anakinra and/or placebo will be given on site and 4 syringes of anakinra and/or placebo will be dispensed for 2 days of treatment at home at 24 and 48 hours. At Visit 2 (Day 4), 2 injections of anakinra and/or placebo will be given on site and 2 syringes of anakinra and/or placebo will be dispensed for 1 day of treatment at home at Day 5. At Visit 2 (Day 4) and Visit 3 (Day 8), unused syringes will be returned.

For patients randomized to anakinra 100 mg, one syringe will contain 100 mg anakinra and one syringe will contain placebo.

For each day, the number of used syringes will be recorded (in the CRF if on site and in the eDiary if at home). For anakinra, the pair of syringes are numbered 1 and 2 and is randomly linked to anakinra or placebo. If only a single syringe is used, its number is recorded.

The number of dispensed syringes for use at home and the number of returned unused syringes are recorded in the CRF dispense log.

Anakinra:

- Total amount given for one flare will be calculated as number of syringes containing Anakinra used\*100 mg.
- If a treatment at home is not recorded in the diary but no corresponding unused syringes are returned, it is assumed that the syringes were used (If the number of syringes injected as recorded in the eDiary is less than unused syringes returned recorded in CRF dispense log, the number of syringes used for the flare will be updated to match the dispense log.)
- If a patient, randomized to anakinra 100 mg, has only used a single syringe the number of the syringe will be taken into account, i.e. dependent on if the number is linked to anakinra or placebo, 100 mg or 0 mg will be used in the exposure calculation. If there is no information which syringe was used, it is assumed to be anakinra 100 mg.

Triamcinolone: Total amount for one flare is the same as the exposure at Day 1, and if dose is recorded as administered in the CRF the exposure is 40 mg for that flare.

## 18.24 Adverse event start/stop day

The start day of an AE will be linked to the specific flare, and is defined as:

*Start date of adverse event – Date for 1st IMP injection for latest flare + 1*

where the date for 1st IMP injection for latest flare is based on the latest flare prior to start of the specific AE.

The stop day of an AE is defined as:

*Stop date of the adverse event – Date for the 1st IMP injection for the latest flare + 1*

where the date for the 1st IMP injection for the latest flare is based on the latest flare prior to the start of the specific AE.

For AEs starting within 72 hours after the 1st IMP administration for the latest flare, the start hour will also be calculated and is defined as:

*Start date/time hour of adverse event – Date/time hour for 1st IMP injection for latest flare*

In addition for the subsequent flares the start and stop dates will also be calculated from the date for the 1st IMP injection for the 1st flare.

In case of incomplete or missing start date, the following rules will be applied:

- If the day is missing, and the month and year is the same as for the date for 1st IMP injection for the latest flare, the start date will be set to the date for 1st IMP injection for the specific flare. Otherwise the date will be set to YYYY-MM-01.
- If day and month are missing, and the year is the same as for the date for the 1st IMP injection for the first flare, the start date will be set to the date for 1st IMP injection for the specific flare. Otherwise the date will be set to YYYY-01-01.
- If day, month and year are missing, the start date will be set to the date for the 1st IMP injection for the first flare, i.e. baseline visit.

In case of incomplete or missing stop date for a resolved AE, the following rules will be applied:

- If the day is missing, the stop date will be set to the last day of the month, i.e. YYYY-MM-30/31 if this date becomes before the end of study date, otherwise the date will be set to end of study date.
- If day and month is missing, the stop day will be set to YYYY-12-31 if this date becomes before the end of study date, otherwise the date will be set to end of study date.
- If day, month and year is missing, the AE will be set to ongoing.

## 18.25 Treatment emergent abnormal vital signs

Treatment emergent vital signs are defined as: Values that are normal or high at baseline for each flare and shift to low at the corresponding visit, or that are normal or low at baseline and shift to high at the corresponding visit.

The normal reference ranges used are:

- Systolic blood pressure (mmHg): 100 to 140
- Diastolic blood pressure (mmHg): 60 to 90
- Pulse rate (beats/min): 50 to 90

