5.1.4.2 Safety

The safety profile of anakinra is well established. Since its approval in the US 2001 for the treatment of RA, it is calculated that, up to 01 May 2016, the total post-marketing exposure is 84 408 patient-years.

In placebo-controlled studies in RA patients, the most frequently reported adverse reactions were injection-site reactions (ISRs), which were mild to moderate in most patients. From studies in RA there are indications that ISRs are more frequent when daily doses of >100 mg s.c. are administered. In RA studies, the vast majority of ISRs occurred within the first 4 weeks of therapy. Less than 20% of the ISRs occurred during the first 5 days, also when daily doses of >100 mg were administered.

The incidence of serious adverse events (SAEs) at the recommended dose in RA (100 mg/day) was comparable with placebo. The incidence of serious infections was higher in anakinra-treated patients with RA compared to patients receiving placebo (2 % vs. < 1 %). In clinical studies and during post-marketing use, rare cases of opportunistic infections have been observed including fungal, mycobacterial, bacterial, and viral pathogens. In clinical studies of RA, neutropenia (absolute neutrophil count (ANC) <1 x 10⁹/L) occurred in 0.4 % of patients receiving anakinra.

Repeated short-term administration of anakinra has not been previously studied. This type of administration could possibly result in an increased risk for development of ADA, which may result in an increased risk for allergic/anaphylactic reactions, ISRs or reduced efficacy. The occurrence of ADA against anakinra has been evaluated in clinical studies in RA, and no correlation between ADA development and AEs has been observed.

In an open-label study in NOMID (the most severe form of CAPS), patients were treated with anakinra up to 5 years. The safety profile was similar to the safety profile observed in studies of patients with RA, with the exception of the ISR frequency which was comparable to the ISR frequency of placebo-treated patients in RA studies.

In previous clinical studies of sepsis, more than 1000 patients received anakinra i.v. at doses up to 2 mg/kg/hour over a 72-hour treatment period. The safety profile in these studies was similar to that seen in other indications (33, 34, 35). The maximum tolerated dose of anakinra has not been established in humans.

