Unsuitable for or contraindicated or not appropriate for treatment with	
 • Uncontrolled hypertension (w/wo anti-HTN medications and SBP\geq140 mm Hg or DBP\geq90 mm Hg) ¹ • Cardiovascular disease; history of angina, ischemia, positive stress test or MI • Heart failure • Impaired renal function (eGFR <60mL/min/1.73m²) • Concurrent use of thiazide diuretics and/or an ACE inhibitor or angiotensin receptor II antagonists, especially in CKD • Current treatment with anticoagulants • Gastroesophageal disease (GERD with prescribed h2 receptor antagonist or PPI or documented PUD or history of upper GI bleed) • Active or latent peptic ulcer/GI bleed (specifically in elderly patients) • Hypersensitivity (should not be given to patients who have experienced asthma, urticaria, or allergic-type reactions after taking aspirin (acetyl salicylic acid) or NSAIDs) • Conditions with increased risk for bleedings including hematological disease • Inflammatory bowel disease (IBS) 	
 • Patients with renal or hepatic impairment should not be given colchicine in conjunction with P-gp or strong CYP3A4 inhibitors • Potential toxicity due to PK/PD drug interactions especially in conjunction with p-gp or CYP3A4 inhibitors (e.g., diltiazem, verapamil, clarithromycin and cyclosporin), concurrent use of simva-, atorva-, and fluva-, and pravastatin • Gout attack onset \geq36 hours prior to treatment initiation • Patients on prophylactic colchicine treatment already and have received acute gout treatment regimen with colchicine within 14 days

HTN=hypertension SBP=systolic blood pressure DBP=diastolic blood pressure MI=myocardial infarction eGFR= estimated glomerular filtration rate ACE=angiotensin converting enzyme CKD=chronic kidney disease GERD=gastroesophageal reflux disease PPI=proton pump inhibitor PUD=peptic ulcer disease GI=gastro-intestinal P-gp=P-glycoprotein CYP=Cytochrome P-450 PK=pharmacokinetic PD=pharmacodynamics IBS=irritable bowel syndrome

Appendix 6

Signs of unresponsiveness to NSAIDs and colchicine treatment of gouty arthritis flares. The list includes examples and are not limited to the conditions listed below.

	NSAIDs	Colchicine

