### **16.3 Laboratory data**

The presentations will be based on the results from the central laboratory safety data.

The laboratory safety data will be presented as actual values at baseline, 72 hours, Day 8 and Day 15 and changes from baseline at 72 hours, Day 8 and Day 15 for each flare by descriptive statistics.

The number and percentage of patients with low, normal, or high laboratory values at baseline versus 72 hours, Day 8 and Day 15 for the first flare will be presented using shift tables. For subsequent flares the number and percentage of patients with low, normal, or high laboratory values at baseline for the flare of interest versus Day 15 will be presented using shift tables.

The values at 72 hours, Day 8 and Day 15 versus baseline for the flare of interest for each laboratory parameter for each flare will be presented in a scatterplot. Side by side plots for anakinra (different symbols for 100 mg and 200 mg) and triamcinolone will be performed.

Treatment emergent abnormal laboratory values will be listed. Values that are normal or high at baseline for each flare and shift to low at the corresponding visit, or that are normal or low at baseline and shift to high at the corresponding visit.

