### **16.4 Vital signs**

Vital signs (blood pressure, pulse rate and body temperature) will be presented as actual values at baseline, 72 hours, Day 8 and Day 15 for each flare by descriptive statistics.

Treatment emergent abnormal vital signs will be listed. Values that are normal or high at baseline for each flare and shift to low at the corresponding visit, or that are normal or low at baseline and shift to high at the corresponding visit will be listed. See Section 18.25 for definition of low, normal and high.

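### The treatment-emergent rule has no temperature range and never lists same-direction worsening from an abnormal baseline, and later-flare laboratory shift tables use Day 15 only

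*SAP*

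**What the plan says.** **Vital signs.** SAP 16.4 says "Vital signs (blood pressure, pulse rate and body temperature) will be presented as actual values at baseline" and at 72 hours, Day 8 and Day 15 of each flare. It then plans a listing of treatment-emergent abnormal values and refers to 18.25 for what counts as low, normal or high.

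**The rule.** Under SAP 18.25 the listing takes in any fall into the low category by a patient who began the flare in one of the other two. Its second limb, for rises, reads: "or that are normal or low at baseline and shift to high at the corresponding visit". The section gives three ranges: "Systolic blood pressure (mmHg): 100 to 140", diastolic pressure 60 to 90 mmHg, and "Pulse rate (beats/min): 50 to 90". Body temperature has no range there or elsewhere in the two documents.

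**Laboratory data.** SAP 16.3 uses the same category rule for its treatment-emergent listing. First-flare shift tables compare baseline with 72 hours, Day 8 and Day 15. For subsequent flares, "laboratory values at baseline for the flare of interest versus Day 15 will be presented using shift tables". Protocol 7.5.6.2 has samples taken at all three post-baseline visits of every flare.

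**The concern.** A listing that SAP 16.4 promises cannot be produced for one of its own variables. Temperature bears on infection, a risk the protocol itself reports in section 5.1.4.2: "The incidence of serious infections was higher in anakinra-treated patients with RA compared to patients receiving placebo" (2 % against less than 1 %).

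The rule also looks only at changes of category. A patient who starts a flare with a high value cannot be listed for a further rise, whatever its size. This can arise in the population enrolled: Protocol Appendix 5 gives "Uncontrolled hypertension (w/wo anti-HTN medications" and systolic pressure of at least 140 or diastolic of at least 90 mmHg) and eGFR below 60 as examples of why NSAIDs may be unsuitable, which feeds inclusion criterion 8. Baseline is reset at each flare, so a patient who has become high by the start of a later flare falls into the same gap.

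Finally, Protocol 7.2.1 says the extension is mainly about safety and immunogenicity, and 5.1.4.2 says repeated short courses have not been studied before. Later flares are nevertheless where the laboratory shift tables are thinnest.

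**Working it through.** The plan states no figure on this point, so there is none to reproduce. The check applies the rule as written and sets the planned outputs side by side.

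**Inputs**
- Ranges (SAP 18.25): systolic 100–140 mmHg, diastolic 60–90 mmHg, pulse 50–90 beats/min. I take the limits as normal; the SAP does not say.
- Rule (SAP 18.25, same in 16.3): list if baseline is normal or high and the visit is low, or if baseline is normal or low and the visit is high.
- Post-baseline visits, every flare (Protocol 7.5.6.2 and 7.5.6.3): 72 hours, Day 8, Day 15.
- Subcutaneous dosing: Days 1 to 5 (Protocol 7.4.6.2).

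**Step 1: all category pairs**

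| Baseline | Visit low | Visit normal | Visit high |
|---|---|---|---|
| Low | not listed | not listed | listed |
| Normal | listed | not listed | listed |
| High | listed | not listed | not listed |

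Four of 3 × 3 = 9 pairs are listed. High to high and low to low never are.

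**Step 2: illustrative values against the SAP ranges**

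| Variable | Baseline → visit | Listed? |
|---|---|---|
| Systolic (mmHg) | 140 → 141 | yes |
| Systolic (mmHg) | 141 → 200 | no |
| Systolic (mmHg) | 99 → 70 | no |
| Systolic (mmHg) | 150 → 99 | yes |
| Diastolic (mmHg) | 91 → 120 | no |
| Pulse (beats/min) | 91 → 140 | no |
| Pulse (beats/min) | 49 → 35 | no |
| Temperature (°C, assumed values) | 36.8 → 39.5 | cannot be classified |

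A change of 1 mmHg is listed and one of 200 − 141 = 59 mmHg is not. Laboratory examples cannot be computed, because the documents do not give laboratory reference ranges.

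**Step 3: what else is planned for each flare (SAP 16.3, 16.4)**

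| Output | Laboratory | Vital signs |
|---|---|---|
| Actual values, 72 h, Day 8, Day 15 | yes | yes |
| Change from baseline, same visits | yes | no |
| Scatterplot against baseline, same visits | yes | no |
| Shift table, first flare | 72 h, Day 8, Day 15 | none |
| Shift table, later flares | Day 15 | none |
| Treatment-emergent listing | yes, each visit | yes, except temperature |

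**Step 4: later-flare shift visits.** Three post-baseline samples are collected and one is used, so 3 − 1 = 2 are left out. The 72-hour sample falls on Day 4, the only one within Days 1 to 5. Day 8 and Day 15 fall after dosing has ended.

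**The case against.** The strongest reply is that little is hidden. SAP 9 defines descriptive statistics to include minimum and maximum, so a systolic pressure of 200 mmHg or a temperature of 39.5 °C would appear as the maximum for that arm, visit and flare. Protocol 9.3.6 puts all data in patient listings. Protocol 7.5.6.2 and 7.5.6.3 turn clinically significant abnormal values into adverse events, and SAP 16.2 counts patients with such events by treatment group, for each flare and overall. Laboratory values and changes are summarized and plotted at all three visits of later flares, and the laboratory listing is not confined to Day 15. Defining treatment-emergent as entry into a new category is coherent. Safety analysis here is descriptive, in an exploratory Phase 2 trial.

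Most of this stands and limits the point. A reader might infer that adverse event reporting gives no count by arm; SAP 16.2 shows that it does. A reader might also infer from Appendix 5 that most patients start with high blood pressure. The documents do not support that: hypertension is one of 11 NSAID examples in a non-exhaustive list, either pressure component alone meets it, a separate colchicine criterion must also be met, a systolic value of exactly 140 mmHg is normal under 18.25, and no baseline share is given.

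Three things survive. The temperature listing cannot be produced. A maximum at a visit is not tied to that patient's baseline, and does not show how many patients worsened. The adverse event route depends on the investigator's judgement, so values not reported as events are not counted there.

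**Conclusion.** The point holds as a defect in flagging and tabulation; it does not mean that safety data are lost or left unanalysed.

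- **Temperature:** the planned listing cannot be executed. This rests only on reading 16.4 against 18.25.
- **Same-direction worsening:** never listed, for vital signs or laboratory values. The gap is wider for vital signs, where worsening shows only in actual-value summaries, patient listings, or adverse events if judged clinically significant. Laboratory changes from baseline and scatterplots narrow it for laboratory data.
- **Later-flare laboratory shifts:** two of three collected visits are left out, including the only one during dosing. What is missing is the by-arm category-shift count at 72 hours and Day 8.

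The number of patients affected cannot be estimated from the documents. The primary analysis and sample size are untouched. The change is worth making because these are stated rules that weaken a safety output, and better ones need no new data.

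**What to change.** - **SAP 18.25:** add a body-temperature reference range, chosen by the sponsor before the first database lock.
- **SAP 16.4:** add change from baseline at 72 hours, Day 8 and Day 15 for each flare. Also list values that start outside the range and move further out in the same direction by a margin the sponsor fixes before that lock. The timing matters because the sponsor receives unblinded data afterwards (SAP 4.3). The same clause could be carried into the laboratory listing in 16.3, where the need is smaller.
- **SAP 16.3:** give subsequent flares the same 72-hour, Day 8 and Day 15 shift tables as the first flare, plus the worst post-baseline value.
- **Optional:** counts of patients with ANC below 1.5 and below 1.0 × 10⁹/L by arm and flare. In the protocol these are an eligibility limit and a background figure from RA studies, not planned analysis thresholds.

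All data are already collected and existing table programs can be reused. The cost is SAP wording, a longer listing and more table pages.
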